3.3 Justification of dose

Efficacy of SLIT-drops has been found to be dose-dependent in clinical trials where the dose was increased gradually from 50 to 150 SRU/day over 10 days to reach the minimum recommended maintenance dose of 300 SRU (see section 8.1) (Braun et al. 2010). This up-dosing titration schedule will be used for the current trial and was previously assessed with *Phleum pratense* OSIRIS[®] sublingual solution and found to be well-tolerated(Nittner-Marszalska et al. 2013). Based on the results of immunological data, 300 SRU was established as the optimal tested dose for maintenance treatment. The 300 SRU dose is currently used in daily clinical practice (Didier et al. 2015) because it is considered safe and efficient (Canonica et al. 2009).

3.4 End of trial definition

A subject is considered to have completed the trial if he/she has completed the last scheduled visit (V9).

The end of the trial is defined as the date of the last follow-up phone visit (TC follow-up) for the last subject in the trial.

Clinical trial protocol	Date:	12-Nov-2021	
Trial ID: SU-G-01	Version:	4.0	
EudraCT No. 2020-000455-12	Status:	Final	
CONFIDENTIAL	Page:	28 of 77	

4 TRIAL POPULATION

Subjects randomised in this trial will be adults ≥18 years of age, with a clinical history of allergic rhinoconjunctivitis (with or without asthma) as diagnosed by a physician and having had symptoms despite treatment with antihistamines or nasal steroids during the two previous grass pollen seasons.

Subjects meeting all the inclusion criteria and none of the exclusion criteria will be considered eligible for the trial.

4.1 Inclusion criteria

Subjects are eligible to be included in the trial only if all the following criteria apply:

- 11. Written informed consent obtained before any trial related procedures are performed
- I2. Male or female aged \geq 18 years on the day informed consent is obtained
- 13. For female subjects of childbearing potential,⁹ a negative pregnancy test and willingness to practice appropriate contraceptive methods¹⁰ until the follow-up visit must be confirmed
- I4. A clinical history of grass pollen-induced allergic rhinoconjunctivitis for two years or more with or without asthma¹¹
- 15. A clinical history of severe allergic rhinoconjunctivitis symptoms (interfering with usual daily activities or sleep) induced by grass pollen, which remain troublesome despite symptomatic treatment with antihistamines, nasal steroids or eye drops during the previous grass pollen season
- I6. Positive specific immunoglobulin E (IgE) (defined as ≥class 2, ≥0.70 kU/I) against grass: *Phleum pratense*
- 17. Positive skin prick test (SPT)¹² to Phleum pratense at screening
- 18. The subject must be willing and able to comply with the trial protocol

⁹ Females, after the first menstrual period. Females who are post-menopausal are considered not to be of child-bearing potential. A postmenopausal state is defined as no menses for 12 months without an alternative medical cause.
¹⁰ For the purpose of this protocol the following contraceptive methods are considered appropriate: oral contraceptives, transdermal

¹⁰ For the purpose of this protocol the following contraceptive methods are considered appropriate: oral contraceptives, transdermal patches or depot injection of a progestogen drug (starting at least 4 weeks prior to IMP administration); double barrier method: condom or occlusive cap (diaphragm or cervical/vault caps) plus spermicidal agent; IUD, IUS, implant, or vaginal ring (placed at least 4 weeks prior to IMP administration); or male partner sterilisation (vasectomy with documentation of azoospermia) prior to the female subject's entry into trial and is the sole sexual partner for that female subject. Sexual abstinence is acceptable as contraceptive if it is true abstinence and in line with the usual lifestyle of the subject. Periodic abstinence (e.g. calendar, ovulation, symptothermal, post-ovulation methods) and withdrawal are not acceptable methods of contraception. *However, national requirements regarding contraception should always be followed.*

¹¹ If medical records are not available, verbal history from subject can be used to fulfill this criterion and this must be documented in the medical records by the investigator.

¹²A positive Skin Prick Test (SPT) is defined in the SPT Guideline. For subjects in Europe, a positive SPT is defined as a wheal size \geq 3 mm. If medication that could interfere with the skin prick test, according to Table 7 has not been washed out and the positive control is <3 mm for subjects in Europe, the skin prick test can be repeated after the interfering medication has been washed out.

Clinical trial protocol	Date:	12-Nov-2021	
Trial ID: SU-G-01	Version:	4.0	
EudraCT No. 2020-000455-12	Status:	Final	
CONFIDENTIAL	Page:	29 of 77	

4.2 Exclusion criteria

Subjects are excluded from the trial if any of the following criteria apply:

- E1. Previous participation in this trial. Participation is defined as screening
- E2. Has a clinically relevant history of symptomatic seasonal and/or perennial allergic rhinoconjunctivitis and/or asthma caused by an allergen other than grass pollen, to which the subject is exposed, which could potentially overlap with the efficacy assessment periods
- E3. Within the last 3 months before the randomisation visit, has had an occurrence of any clinical deterioration of asthma that resulted in emergency treatment, hospitalisation, or treatment with systemic corticosteroids
- E4. Reduced lung function: FEV₁ <70% of predicted value after adequate pharmacologic treatment¹³
- E5. SLIT treatment with any grass pollen AIT for more than 1 month within the last 5 years. In addition, any SLIT treatment with grass pollen AIT within the previous 12 months
- E6. SCIT treatment with any grass AIT reaching the maintenance dose within the last 5 years. In addition, any SCIT treatment with grass AIT within the previous 12 months
- E7. Ongoing treatment with any allergy immunotherapy product
- E8. Uncontrolled or severe asthma requiring daily use of more than 800 mcg budesonide or equivalent at screening
- E9. Severe chronic oral inflammation
- E10. Any nasal or naso/oropharyngeal condition that could confound the efficacy or safety assessments (e.g. hypertrophy of the pharyngeal/palatine tonsils, clinically relevant nasal polyps, a history of paranasal sinus surgery or surgery of nasal turbinates)¹⁴
- E11. Has a diagnosis of eosinophilic oesophagitis
- E12. At randomisation, current symptoms of, or treatment for, upper respiratory tract infection, acute sinusitis, acute otitis media or other relevant infectious process (serous otitis media is not an exclusion criterion)
- E13. A relevant history of systemic allergic reaction e.g. anaphylaxis with cardiorespiratory symptoms, generalised urticaria or severe facial angioedema that in the opinion of the investigator may constitute an increased safety concern
- E14. Any clinically relevant chronic disease incl. malignancy that in the opinion of the investigator would interfere with the trial evaluations or the safety of the subject
- E15. Active or poorly controlled autoimmune diseases, immune defects, immunodeficiencies, immunosuppression or malignant neoplastic diseases with current disease relevance
- E16. Immunosuppressive treatment (ATC code L04 or L01) ≤ 90 days prior to the screening visit

¹³ Lung function will be measured according to the ATS/ERS spirometry recommendations (Reddel et al. 2009). The subjects will be included based on spirometry values measured at the site and reported by the site according to the site's pre-programmed spirometric reference equations. The reference equations and values used should be documented on every pulmonary function report.

¹⁴ If in doubt, nasal endoscopy is recommended

Clinical trial protocol	Date:	12-Nov-2021	
Trial ID: SU-G-01	Version:	4.0	
EudraCT No. 2020-000455-12	Status:	Final	
CONFIDENTIAL	Page:	30 of 77	

- E17. Treatment with medications with potential impact on efficacy endpoints (e.g. treatment with anti-IgE drugs within 130 days/5 half-lives of the drug (which ever longest) or treatment with antidepressant or antipsychotic medications with antihistaminic effect)
- E18. A history of allergy, hypersensitivity or intolerance to the IMP (except to the active ingredient) or any of the background treatment provided in this trial
- E19. Female who is pregnant or breast-feeding
- E20. Has a business or personal relationship with trial staff or sponsor who is directly involved with the conduct of the trial

4.3 Screen failures

Screen failures are defined as subjects who consent to participate in the clinical trial but are not eligible for participation according to in/exclusion criteria and subsequently not randomly assigned to trial intervention/entered in the trial. A minimal set of screen failure information is required to ensure transparent reporting of screen failure participants in order to meet the Consolidated Standards of Reporting Trials (CONSORT) publishing requirements and to respond to queries from regulatory authorities. Minimal information includes demography, medical history, adverse events, eligibility criteria and screen failure details.

4.3.1 Rescreening

Screen failures may not be rescreened.

5 SUBJECT DISCONTINUATION

5.1 Discontinuation from IMP treatment

Subjects must be discontinued from IMP treatment under the following circumstances:

- If a subject becomes pregnant
- The subject experiences severe or persistent symptoms of oesophagitis or has a confirmed diagnosis of eosinophilic oesophagitis
- The subject's asthma becomes difficult to control
- If, in the investigator's opinion, continuation with IMP treatment would be detrimental to the subject's well-being
- If treatment is unblinded for the subject or investigator

For all subjects discontinued from IMP, efforts must be made to have subjects attend and complete all scheduled visit procedures to collect the data for the primary and key secondary endpoints. Subjects must be educated about the scientific importance of their data, even if they discontinue trial product.

5.2 Discontinuation from trial

The subject will be advised in the informed consent form that he/she has the right to discontinue from the trial at any time without prejudice.

Subjects must be discontinued from the trial under the following circumstances:

Clinical trial protocol	Date:	12-Nov-2021	
Trial ID: SU-G-01	Version:	4.0	
EudraCT No. 2020-000455-12	Status:	Final	
CONFIDENTIAL	Page:	31 of 77	

- If, in the investigator's opinion, continuation in the trial would be detrimental to the subject's well-being
- If informed consent is withdrawn

If found required by ALK after discussion with the investigator, subjects may be discontinued from the trial under the following circumstances:

- If subject is treated with prohibited medication as defined in Table 2
- In case of protocol deviation, violation of eligibility criteria or deviation from the treatment plan specified in the protocol (e.g. incorrect administration of the IMP)
- Simultaneous or previous participation (within 30 days of randomisation) in other clinical trials of an approved or non-approved investigational medicinal product

In case a subject discontinues from the trial, the discontinuation page in the electronic case report form (eCRF) should be completed. On the discontinuation page the investigator should record the date of the discontinuation from the trial, the person initiating the discontinuation, and the primary reason for discontinuation. If an adverse event (AE) is involved in a discontinuation, this must be recorded as the primary reason. In all cases, the primary reason for discontinuation must be recorded in the eCRF and in the subject's medical records. A follow-up visit on the subject is necessary to establish trial-related AEs that must be reported in accordance with the appropriate procedures.

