During the trial, data will be entered in an eDiary by the subject and transferred to the eDiary vendor database on a daily basis. If the subject has missed more than 2 days in a row the investigator/designee will be notified by email and must contact the subject. In addition, if the total compliance for a period is less than 80% the investigator/designee must contact the subject and retrain the subject in the use of the eDiary. The aim is for the overall compliance for a subject in the trial not to be below 80%.

There will be no other source documentation for these data other than the vendor database.

After database lock, all access to the eDiary will be set as "read only". The sponsor will extract blinded data from the eDiary system. The investigator will be provided with an electronic copy of the diary data collected at the specific site at the latest 3 months after end of trial, by the vendor. The eDiary data will be subject to periodic review by the sponsor. Findings during the review of the eDiary data will be evaluated by the investigator and updates/correction to the data can only be executed by the investigator or if raised by sponsor only executed after confirmation and approval by the investigator.

Documentation of the data load from the eDiary vendor to ALK will be described in the data management report.

Clinical trial protocol	Date:	12-Nov-2021	
Trial ID: SU-G-01	Version:	4.0	
EudraCT No. 2020-000455-12	Status:	Final	
CONFIDENTIAL	Page:	55 of 77	

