15.1.3 Secondary estimand

Using the framework proposed in the ICH E9(R1) addendum (ICH 2020), the treatment policy estimand can be described by:

- A. Treatment: 5-grass mix SLIT-drops, where rescue medication is taken as required.
- B. Population: Subjects randomised in this trial will be adults ≥18 years of age, with a clinical history of allergic rhinoconjunctivitis (with or without asthma) as diagnosed by a physician and having had symptoms despite treatment with antihistamines or nasal steroids during the two previous grass pollen seasons
- C. **Variable**: Average total combined score (TCS) during the 2nd PGPS
- D. **How to account for intercurrent events:** regardless of whether subjects complete treatment for the planned duration (treatment policy strategy)
- E. Population summary: Absolute difference in means between treatment conditions

A treatment policy strategy will be used to address the intercurrent event of discontinuation of trial treatment. As such, if a subject discontinues trial treatment, all available diary data will be included in the analysis, regardless of adherence to treatment. Details of the handling of IEs and missing data are provided in Section **15.11.3**.

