15.2 Sample size and power considerations

General considerations:

In this trial, primary and secondary endpoints are tested hierarchically to control the family-wise error rate at 5% level. Individual endpoint analyses are based on treatment comparisons using a 2-sided t-test on a 5% level of significance.

The power calculations were done in two steps. The initial sample size calculation was done for observed cases only. This sample size is then evaluated using the estimand framework. The power is calculated for both the primary endpoint (TCS) and the key secondary endpoint (RQLQ). It is expected that the treatment difference in RQLQ is greater than the minimal clinically important difference (MCID) (0.16).

TCS power calculation:

The estimated TCS mean, standard deviation and treatment differences during the peak season from three trials is presented in **Table 8**. The power calculation is based on a TCS treatment difference of 21% (1.64 in absolute value) and a common standard deviation of 5.5. Under these assumptions, the trial has a power of 80% with the sample size of 180 evaluable subjects. The power will be 86% for the primary estimand and 80% for the secondary estimand with the assumption that 10% out of 220 subjects will discontinue the trial, with 4.5% of subjects discontinuing due to adverse events and 1% due to lack of efficacy each year.

Table 8	Mean and standard deviation of TCS during the peak of a season.
---------	---

Trial	Placebo μ (σ)	Active μ (σ)	Difference Absolute (relative)
GT-08 2006	8.44 (5.48)	5.14 (4.06)	3.3 (39%)
P05238	7.74 (6.50)	6.10 (5.09)	1.64 (21%)
P08067	5.73 (5.03)	4.56 (4.60)	1.17 (20%)
Average			2.04

RQLQ power evaluation:

The estimated RQLQ mean, standard deviation and treatment differences during the peak season from 3 trials raw data is presented in **Table 9**.

Table 9Mean and standard deviation of RQLQ during the peak of a season.

Trial	Placebo	Active	Difference
	μ (σ)	μ (σ)	Absolute (relative)
GT-08 2005	1.82 (1.11)	1.37 (0.97)	0.45 (25%)

Clinical trial protocol	Date:	12-Nov-2021	ALK
Trial ID: SU-G-01	Version:	4.0	
EudraCT No. 2020-000455-12	Status:	Final	
CONFIDENTIAL	Page:	59 of 77	

GT-08 2006	1.48 (1.05)	1.05 (0.91)	0.43 (29%)
P05238	1.73 (1.34)	1.41 (1.12)	0.33 (18%)
P08067	1.32 (1.11)	1.18 (1.08)	0.15 (11%)
Average			0.34

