6.1.2 IMP discontinuation

As pointed to previously, reasons for discontinuation of IMP will be categorised into three categories: 1) due to "IMP-related AE" 2) due to "lack of efficacy" and 3) due to "other reasons". As the eCRF defined that trial- and treatment discontinuation reasons are not corresponding to this tripartite split the following mapping form the observed data in the eCRFs to the three categories will be performed:

Treatment discontinuation reasons presented in the eCRF's "Visit Status"-form are:

• Severe or persistent symptoms of eosinophilic oesophagitis

- Pregnancy
- Physician's decision
- Adverse event(s)
- Asthma difficult to control
- Treatment is unblinded

while withdrawal from trial reasons presented in eCRF's "End of study"-form are:

- Screening failure
- Withdrawal of consent
- Adverse event(s)
- Lost to follow-up
- Non-compliance with protocol
- Pregnancy
- Death
- Lack of efficacy
- Randomisation code broken
- Other

Before DBL, the discontinuation of treatment is re-defined and the subject specific list of discontinuations and their classifications to fit the estimand framework is in supplementary document to the SAP: Documentation of Trial Analysis Sets.

Discontinuation due to AEs

A subject is considered discontinued from the treatment due to IMP-related AE if the following conditions are met:

- 1. If, in the "Visit status"-form or End of study"-form reported reason for treatment discontinuation or withdrawal from trial is:
 - Severe or persistent symptoms of eosinophilic oesophagitis
 - Adverse event(s)
 - Asthma difficult to control
- 2. And AEs related to discontinuation are classified as possibly or probably related.

Discontinuation due to lack of efficacy

A subject is considered discontinued from the treatment due to lack of efficacy if the following conditions are fulfilled:

1. If, in the "End of study"-form, it is noted that the subject withdrawal from trial due to "Lack of efficacy".

Discontinuation due to "other reasons"

A subject is considered discontinued from the treatment due to other reasons if the subject discontinues treatment or withdrawal from trial due to other reasons than mentioned above.

Date: 27-Oct-2023 Version: 1.0 Status: Final Page: 21 of 47

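### Protocol 5.2 allows the sponsor to end a subject's trial follow-up for prohibited medication or a deviation, which stops collection of diary data that the treatment policy estimand needs

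*Protocol*

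**What the plan says.** Protocol 5.2 separates mandatory from optional discontinuation from the trial. The optional list applies when the sponsor finds it required after discussion with the investigator. It opens with "If subject is treated with prohibited medication as defined in Table 2" and goes on to protocol deviation, violation of eligibility criteria and departure from the treatment plan.

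Protocol 5.1 deals with stopping IMP. For those subjects, "efforts must be made to have subjects attend and complete all scheduled visit procedures to collect the data for the primary and key secondary endpoints". Section 5.2 has no matching sentence for subjects taken out of the trial.

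For the treatment policy estimand, Protocol 15.1.3 says that "all available diary data will be included in the analysis, regardless of adherence to treatment". SAP 3.1.1.3 adds that its main feature is that subjects complete the trial, even if no longer on IMP. Its data set, DPS2 (SAP 5.2), covers assessments made while the subject is in the trial.

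SAP 6.1.2 lists "Non-compliance with protocol" among the withdrawal reasons. Neither the AE rule nor the lack-of-efficacy rule captures it, so it drops into other reasons. SAP 6.2.1 and 6.2.3, with Tables 5 and 7, impute that category from the subject's own arm as missing at random.

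**The concern.** An estimand defined whatever the adherence needs outcome data on subjects who did not adhere. Section 5.2 gives the sponsor an option to stop collecting those data because of non-adherence. This is missingness that the trial's own rules can create, and the party holding the option also sees outcomes as they accrue: "The eDiary data will be subject to periodic review by the sponsor" (Protocol 14.2).

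The loss may be informative. Some Table 2 products relieve allergy symptoms, and a subject who takes one in season, on top of the permitted rescue medication, may be doing worse than others in the same arm. The imputed value is a draw by arm, season and ongoing asthma status, so in expectation such a subject receives a typical score for the arm. An active subject would be credited with more benefit than experienced, and a placebo subject with a better score than the true one. At stake is whether the secondary estimand supports the intention-to-treat reading that Protocol 2.5 and SAP 3.1.1.3 give it.

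**Working it through.** **1. The plan's own power figures.** Protocol 15.2 uses "treatment comparisons using a 2-sided t-test on a 5% level of significance". "The power calculation is based on a TCS treatment difference of 21% (1.64 in absolute value) and a common standard deviation of 5.5", and "the trial has a power of 80% with the sample size of 180 evaluable subjects" (per arm, as its conclusion makes clear).

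- Standard error = 5.5 × √(2/180) = 0.580. Then 1.64/0.580 = 2.829, and 2.829 − 1.960 = 0.869, which gives a power of 80.8% (80.5% with the noncentral t). The stated 80% reproduces.
- Discontinuation is 10% a year, of which 1% is lack of efficacy and 4.5% AEs, leaving 4.5% other by subtraction. Over two years, 1 − 0.9² = 19%: 1.9% lack of efficacy, 8.55% AEs, 8.55% other (about 19 of 220 per arm).
- Primary estimand, lack of efficacy drawn from placebo: 1.64 × (1 − 0.019) = 1.609. With 220 per arm the power is 86.6%, against 86% stated.
- Secondary estimand, AEs also drawn from placebo: 1.64 × (1 − 0.1045) = 1.469, power 80.0%, against 80% stated.

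The two estimand figures reproduce when imputed values count as observed. None of the stated powers is in error on that basis.

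**2. When a removed subject is imputed.** Data obtained before discontinuation are used (Protocol 5.3, in the lost-to-follow-up section). One diary entry in the season period is enough to form the average (Protocol 15.14; SAP 6.2; subject #2 in SAP 6.2.5). The 2nd PGPS endpoint is therefore imputed only if removal precedes every entry in that period.

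**3. Bias from own-arm imputation.** Let fA and fP be the shares of the active and placebo arms removed before the 2nd PGPS. Let e be the excess TCS they would have had over the subjects they are drawn from. Each arm mean is then too low by f × e, and

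bias in the benefit = (fA − fP) × e.

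All three inputs are assumptions, as the documents give none of them. I take e from half to one SD (2.75 to 5.5).

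| fA | fP | Bias | Share of 1.64 |
|---|---|---|---|
| equal | equal | 0 | 0 |
| 5% | 2% | +0.08 to +0.17 | 5% to 10% |
| 2% | 5% | −0.08 to −0.17 | 5% to 10% |
| 8.55% | 0 | +0.24 to +0.47 | 14% to 29% |
| 0 | 8.55% | −0.24 to −0.47 | 14% to 29% |

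The last two rows are extremes: every planned other dropout in one arm is a removal of this kind, and none in the other arm.

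**4. What the planned checks cover.**

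- The treatment policy sensitivity analysis draws all discontinuing active subjects from placebo. That moves an imputed active value by 1.64 on average, which is 1.64/5.5 = 30% of an excess of one SD. Applied to 1% to 8.55% of the active arm it shifts the effect by 0.016 to 0.14. At the upper end the effect is 1.64 × 0.81 = 1.328 and power 71.7%. Placebo subjects are drawn from placebo either way.
- The tipping-point analysis (SAP 6.2.7.1) adds a growing penalty to all imputed active values, whatever the reason, for the primary and first key secondary endpoints. It is run under the trial product main approach only.

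**The case against.** The strongest reply has five parts.

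- **Nothing recorded is lost.** A reader might infer that 5.2 deletes data. It does not: earlier data are kept, the estimand promises available diary data, and many removed subjects could still have an observed endpoint. This stands. What is lost is future data.
- **Sections 5.1 and 5.2 govern different events**, and removal is optional. This also stands, so the conflict is one of purpose rather than of two clashing instructions. It remains a conflict with SAP 3.1.1.3, which expects subjects to complete the trial.
- **Prohibited medication need not mean poor control.** Of 11 product rows in Table 2, about four are symptom relievers (antihistamines, corticosteroids, cromones, decongestants). The others include antidepressants, antipsychotics, immunosuppressants and LABA monotherapy. The argument for informative missingness is therefore confined to in-season symptomatic use, and even there it is an inference.
- **No bias towards active is shown.** A reader might infer one, but the rule applies to both arms, allocation codes are withheld until lock (Protocol 6.2) and the sponsor extracts blinded eDiary data. Unequal removal rates are pure assumption.
- **Confirmatory impact is limited.** Error control applies to the trial product estimand (Protocol 15.10; SAP 4.1), which excludes diary data after IMP discontinuation anyway. Longer follow-up would help it only for subjects still on IMP. This stands; the point bears mainly on the secondary estimand.

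The subject-level classification is in a supplementary document that is not available here, so the mapping to other reasons is a reading of the SAP rule.

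**Conclusion.** The point holds in a limited form. The protocol allows sponsor-initiated loss of outcome data for non-adherence, which does not fit an estimand meant to apply whatever the adherence, and the main analyses treat that loss as unrelated to outcome. The planned checks cover the active arm only, and only in part.

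The number removed, the direction and the size cannot be taken from the documents. With equal rates there is no bias. With a 3-point difference in rates and an excess of half to one SD it is 0.08 to 0.17 TCS points either way. These figures rest on assumed rates and excess, and on every counted subject having no 2nd PGPS entry, so they illustrate and do not estimate. The documents do not support a claim that the result is biased in favour of active treatment.

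**What to change.** **Protocol wording.** Reconcile 5.2 with 5.1 and 15.1.3, so that prohibited medication, a deviation or an eligibility violation does not by itself end eDiary and endpoint follow-up. This concerns data collection only; decisions on IMP and clinical management stay with the existing clinical rules. The cost is a few lines of text and continued diary follow-up of the subjects affected. Last subject last visit was 22-Sep-2023 (SAP 3.2.2), so the edit cannot recover data here and serves later trials.

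**This trial.** Add to SAP 8.3 a table of sponsor-initiated trial discontinuations by arm and reason, showing how many had no 2nd PGPS entry. Protocol 5.2 already has the investigator record who initiated each discontinuation, so no new data are needed. SAP 8.3 plans withdrawal reasons by arm but does not mention the initiator. The cost is one table, which would replace the assumed fA and fP with counts.

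**Not recommended.** Remapping these subjects to lack of efficacy is tempting but does not repair the bias. Placebo subjects are drawn from placebo either way, and active values move by only 1.64. With 3% of placebo and 1% of active removed and e = 5.5, the benefit is understated by 0.02 × 5.5 = 0.11. Remapping adds 0.01 × 1.64 = 0.016, making it about 0.126. Equating prohibited medication with lack of efficacy is also debatable.
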